## Study Design and Participants

### Study design

The time series consists of three phases. The first phase is the preintervention phase – i.e. before the decision support has been implemented. The second phase is the first intervention phase in which the email with recommendations is being sent (Figure 1). The third phase is the second intervention phase in which the real time decision support guidance (Figure 2) is being displayed along with the email intervention.

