## Outcome

### Primary outcome

The adherence to PONV guidelines will be used as the primary outcome. This is defined as an exact match between the recommended and applied numbers of interventions. Either a lower or a higher number of interventions will be considered as noncompliant to the guidelines. For the primary analysis the overall change in adherence as well as the added values of the different decision support elements to that adherence will be quantified. Medications with antiemetic properties will be considered prophylactic administrations, if they occur before the documented anesthesia stop time. We will consider scopolamine, dexamethasone, ondansetron, haloperidol, droperidol as prophylactic medications.

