### Statistical analysis plan

A two-sided alpha of 0.05 will be considered to be statistically significant. Continuous variables will be visually assessed for a normal distribution using histograms and QQ-plots. In descriptive statistics, parametric variables will be expressed as means with standard deviations, nonparametric variables will be expressed as medians with interquartile ranges, and discrete variables will be expressed as numbers with percentages. The primary analysis will be performed under the intention-to-treat principle. We will compare the incidence of the primary and secondary outcomes between the study groups utilizing analysis of variances to compare the means of multiple groups.

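### Decision support is introduced by calendar phase, but the planned ANOVA has no calendar-time error term, so its tests exceed the stated 0.05 if adherence varies from week to week

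*Combined protocol and SAP*

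**What the plan says.** Under Study design, "The time series consists of three phases". Exposure is set by phase: "The first phase is the preintervention phase – i.e. before the decision support has been implemented"; the second phase adds the email; "The third phase is the second intervention phase in which the real time decision support guidance" is shown as well as the email. The documents describe no randomisation and no concurrent control.

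The primary outcome is a yes/no result for each case: "This is defined as an exact match between the recommended and applied numbers of interventions". The same section asks for several contrasts: "the overall change in adherence as well as the added values of the different decision support elements to that adherence will be quantified".

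The Statistical analysis plan section sets the error rate ("A two-sided alpha of 0.05 will be considered to be statistically significant") and covers the whole comparison in one sentence, in which incidences are compared between study groups "utilizing analysis of variances to compare the means of multiple groups". Nowhere do the documents mention calendar week, trend, serial correlation, clustering, robust variance or a mixed model.

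**The concern.** All cases in a given week of a phase have the same exposure, so a phase effect is judged by comparing blocks of calendar time. A one-way ANOVA on cases takes its error term from variation between cases within a phase and treats those cases as independent. If weeks differ in true adherence for any reason unrelated to the intervention, those differences move the phase means but are not properly reflected in their standard errors.

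The comparisons at stake are phase 2 versus 1 (the email), phase 3 versus 2 (the added real-time display) and the overall three-phase comparison. A nominally significant added value could be ordinary weekly fluctuation. Any confidence intervals derived from the ANOVA would be too narrow for the same reason.

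**Working it through.** **Inputs from the documents.** Three consecutive phases, a binary outcome per case, ANOVA between phases, two-sided alpha 0.05. The plan gives no sample size, power or variance figure, so there is nothing of its own to reproduce.

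**Assumed inputs.** True adherence p = 0.40 in every phase, no intervention effect, no trend, m cases per week, and independent weeks with between-week SD tau in true adherence.

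**Formulas.**
- ICC = tau² / [p(1 - p)] = tau² / 0.24
- Design effect D = 1 + (m - 1) x ICC; true SE = sqrt(D) x ANOVA SE
- Actual error rate of a pairwise contrast = 2 x [1 - Phi(1.96 / sqrt(D))]
- Actual error rate of the three-phase test (large-sample chi-square, 2 df) = 0.05^(1/D)

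**Worked case.** With m = 100 and ICC = 0.005, tau = sqrt(0.005 x 0.24) = 0.035 and D = 1 + 99 x 0.005 = 1.495. The SE ratio is sqrt(1.495) = 1.22. The contrast runs at 2 x [1 - Phi(1.96/1.22)] = 10.9% and the omnibus test at 0.05^(1/1.495) = 13.5%.

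| Cases per week | ICC | Week SD (points) | D | Omnibus | Phase 3 vs 2 |
|---|---|---|---|---|---|
| 100 | 0.001 | 1.5 | 1.10 | 6.6% | 6.2% |
| 100 | 0.0025 | 2.4 | 1.25 | 9.1% | 7.9% |
| 100 | 0.005 | 3.5 | 1.50 | 13.5% | 10.9% |
| 100 | 0.01 | 4.9 | 1.99 | 22.2% | 16.5% |
| 200 | 0.005 | 3.5 | 2.00 | 22.3% | 16.5% |

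Simulation with 12 weeks per phase agrees. At 100 cases per week and ICC 0.005 it gives 13 to 14% for the omnibus test and 11 to 12% for the contrast. At ICC 0.01 it gives 21 to 22% and 16 to 17%. With no week variation, both tests run at about 5%.

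**Phase length.** With independent weeks, D does not contain the number of weeks, so longer phases do not help. At 26 weeks per phase (100 per week, ICC 0.005) the simulated rates are 13 to 14% and 10 to 11%.

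**Serial correlation.** At 26 weeks per phase, 100 cases per week and tau = 0.03, the case-level omnibus rate is 11% with independent weeks and 23% with a lag-1 correlation of 0.5.

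**Is it enough to make week the unit?**
- With independent weeks, an ANOVA on weekly proportions returns to about 5%.
- With lag-1 correlation 0.3 (12 weeks per phase, 100 per week, ICC 0.005) it runs at 8.5%.
- With lag-1 correlation 0.5, tau 0.03 to 0.05, 50 to 200 cases per week and 26 weeks per phase, it runs at 10 to 27%.
- With no week variation but a drift of 2 points per year (100 per week, 26 weeks per phase), the case-level ANOVA rejects in 22% of runs and the weekly ANOVA in 21%. At 5 points per year the figures are 92% and 89%.

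The repair therefore needs trend terms and serial correlation as well as a week-level error.

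**The case against.** The strongest reply is that the size rests wholly on assumptions. The documents give no volume, phase length, baseline adherence or between-week variance, and mention nothing that would make weeks differ. With 50 cases per week and a 1-point SD, the contrast runs at only 5.2%. That stands. A reader might infer that the plan's error bars are known to be too narrow, but the documents support only the conditional statement. A reader might also apply an ICC of 0.05 as a rule of thumb. At 40% adherence that implies a week SD of sqrt(0.05 x 0.24) = 11 points, or adherence from about 18% to 62% across two SDs either side. Nothing in the documents supports variation of that size.

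Second, the plan does not name the case as the unit of the ANOVA. That is true, but comparing the incidence of a per-case outcome between groups reads naturally that way. If weeks were intended, the text should say so.

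Third, provider clustering may matter more, since the Hypotheses section has the email sent to individual providers. Provider-clustered errors do not repair week shocks: in a simulation at 12 weeks, 100 cases per week and ICC 0.005, the contrast still ran at 11.7%. That simulation had no provider effect, so a reader should not infer that provider dependence is unimportant. It is a separate source.

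Fourth, the plan promises quantification and does not mention confidence intervals. This narrows the complaint about intervals but leaves the tests at 0.05 affected.

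**Conclusion.** The point holds conditionally. The design assigns exposure by calendar phase, and the stated analysis has no calendar-time error term. For any positive between-week variance, a case-level ANOVA understates the standard errors and exceeds 0.05. The excess is negligible at a week SD of about 1.5 points with 100 cases per week. A week SD of 3.5 to 4.9 points at that volume roughly doubles to quadruples the error rate, and higher volume or serial correlation makes it worse. These sizes assume 40% adherence and, in the table, independent weeks.

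A reader might infer that analysing weekly proportions, with autocorrelation handled only if a residual check flags it, would restore the 0.05 level. That holds only for independent weeks and no drift. The change should be made before analysis, but the documents cannot show how far the planned tests would be off.

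**What to change.** In the Statistical analysis plan section, replace the ANOVA with a segmented (interrupted time series) regression of adherence containing an underlying calendar trend and phase level and slope terms. Specify from the outset an error structure that covers week-to-week variation and serial correlation:

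- weekly proportions weighted by number of cases, with AR(1) or Newey-West errors; or
- a case-level logistic model with an autocorrelated random effect for calendar week, to which a provider random effect can be added.

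Do not make the serial-correlation term depend on a residual test, which has little power in short phases. Take the phase 2 versus 1 and phase 3 versus 2 contrasts, with confidence intervals, from this model. Because slopes are included, state the time point after each changeover to which each contrast refers. Use the same structure for the secondary outcomes, with a suitable distribution for each. State the phase lengths and expected weekly volume.

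The cost is SAP wording and programming, assuming the data warehouse records carry case dates. Intervals will be wider. With 4 weeks per phase, for example, even a simple weekly t-test of two phases has 6 degrees of freedom, and its critical value of 2.45 against 1.96 widens intervals by about 25% when there is no week variation at all. Trend and slope terms would add to that. The error rate of the AR(1) and Newey-West options in short phases was not simulated here and should be checked once phase lengths are known.
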